9.2 Primary Endpoint Analysis

The MRI studies will provide continuous data for the muscle volume (in cm³) of both legs. There will be two volume measurements, one for the lower leg and one for the upper legs at the three timepoints. There will be one spectroscopic measurement which is the ratio of creatine to water in the soleus for all three time points. There are therefore three outcome measures at three time points for each of 15 individuals.

Each outcome measure will be tested for suitability for a one-way repeated ANOVA assessment (checks for outliers, normality, homogeneity and sphericity). If the ANOVA is significant, post-hoc testing will be carried out using Bonferroni correction to identify which timepoints are significantly different. Effect sizes will be calculated.

In the event that the data do not satisfy the criteria for one-way repeated ANOVA, then Friedman's ANOVA will be performed, followed by step-wise post-hoc tests to identify which timepoints are significantly different. Effect sizes will be calculated. All statistics will be performed using IBM SPSS Statistics 24.

Should we establish significant changes in both muscle volume and creatine/water ratio, then we will further investigate the relationship between these changes, bearing in mind the size of this pilot study.

10 Ethics & Regulatory Issues

The conduct of this trial will be in accordance with the ethical principles for medical research involving human subjects determined by the World Medical Association Declaration of Helsinki of the 64th General Assembly in October 2013. All members of the research team and the investigators will be trained in the statutory instrument and those aspects of Good Clinical Practice appropriate to their role in the trial. Favourable ethical opinion and Clinical Trial Authorisation from relevant Competent Authority(ies) will be sought prior to commencement of the trial. Local approvals will be sought before recruitment may commence at each site. Information sheets will be provided to all eligible subjects and written informed consent obtained prior to any trial procedures

11 Confidentiality

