Planned Trial Period	24 months						
	Objective	Outcome Measures					
Primary	Assess change in muscle bulk during the course of therapy	Baseline, 1 month and 6 months investigation with accelerated MRI of selected limb/compartment					
Secondary	 Assess changes in muscle strength and physical function 	 Baseline, 1 month and 6 months: Grip strength Timed rise from chair Gait speed 					
	II. Change in serum biochemistry	 Baseline, 1 month and 6 months: Serum creatinine Serum creatine kinase Serum AST Serum LDH 					

			T
	111.	Change in muscle biochemistry	 Magnetic resonance imaging and spectroscopy of skeletal muscle at baseline, 1 month and 6 months: ratio of total creatine to water; phosphocreatine and inorganic phosphate T2 relaxation time of muscle to measure muscle inflammation.
	IV.	Change in muscle histology and biochemistry	Muscle Biopsy (baseline and 6 months)
	V.	To relate changes in muscle to reduction in systemic inflammation	Baseline, 1 month and 6 month investigations: • Serum CRP • IL-6 • TNF • Interferon • IL1 • IL17
	VI.	To seek any overall changes in body composition	DEXA scan (baseline, 1 month and 6 months)
Exploratory	VII.	Change in serum biochemistry	Baseline, 1 month and 6 month investigations: Serum cystatin C Serum myoglobin
	VIII.	To study tofacitinib's ability to inhibit STAT-3 phosphorylation of IL-6 stimulated peripheral blood mononuclear cells (PBMCs) as a potential response biomarker	 Baseline and 1 month: % change in STAT3 phosphorylation of PBMCs when stimulated with interleukin-6 (IL-6) and tofacitinib added

IX.To measure the change in muscle quality of the upper and lower leg muscle compartmentsBaseline, 1 month a measures of the glo upper and lower leg compartments using	bbal fat fraction of g muscle
---	----------------------------------

GLOSSARY OF TERMS AND ABBREVIATIONS

Acronym Meaning

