2.3 Primary endpoint/outcome

a. Change in skeletal muscle bulk within both lower limbs between baseline, 1 month and 6 months, using compressed sensing (accelerated) MRI.

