2.4 Secondary endpoints/outcomes

- a. Muscle strength and physical function at baseline, 1 month and 6 months, assessed by hand grip, timed rise from a chair and gait speed measurements.
- b. Serum creatinine, creatine kinase, aspartate transaminase and LDH at baseline, 1 month and 6 months.
- c. Magnetic resonance spectroscopy of skeletal muscle: content of creatine, phosphocreatine and inorganic phosphate at baseline, 1 month and 6 months.
- d. Muscle histology and biochemistry at baseline and 6 months.
- e. Circulating CRP and pro-inflammatory cytokines at baseline, 1 month and 6 months.
- f. Body composition at baseline, 1 month and 6 months (assessed by DEXA scan).

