7.3.2 Accelerated MRI and MRS

The Newcastle Magnetic Resonance Centre has developed advanced methodology for measuring tissue energetics (31P MRS) and metabolism (1H MRS) as well as conventional images to measure structure and muscle fat infiltration. MRS is a companion technique to the more familiar magnetic resonance imaging (MRI) scan. It is non-invasive and capable of measuring a broad range of biological compounds across a variety of tissues. In other words, it allows us to study muscle metabolism, which is a point of interest in this trial.

In this trial, the total skeletal muscle volume in the upper and lower leg, covering both legs will be measured using a custom fat-water decomposition MRI, accelerated by compressed sensing methods^{XXXIII}. A custom 3-point Dixon sequence will be used to automatically segment the signals from skeletal muscle, bone and subcutaneous fat. The muscle volume of the upper leg will be delimited from the superior aspect of the greater trochanter to the superior aspect of the patella. The muscle volume of the lower leg will be defined from the superior aspect of the talus to the tibial plateau. This method, developed at Newcastle, is not only faster than conventional T1 weighted imaging but can also be analysed more rapidly. These images will also be used to determine the fat fraction of the upper and lower leg muscle compartments, by measuring the percentage of voxels in which fat predominates (>50% of the voxel) for the same defined anatomic region. To assess muscle inflammation, we will measure the T2 relaxation time by multi-echo spin- echo imaging at mid-lower and mid-upper leg, defined with respect to the bony landmarks above.

We will use PRESS single voxel spectroscopy to examine the relative concentration of creatine to water in the soleus at each time point (voxel size approx. 40 mm x 40 mm x 20 mm)^{xxxiv}. We will use ISIS single voxel spectroscopy to examine the concentration of phosphocreatine, ATP and inorganic phosphate in the soleus.

All MRI assessments will be made at the Newcastle MR Centre on a 3T Philips Achieva dStream Scanner using a 28 channel array coil and a 14cm surface coil for 31P MRS. Measurements obtained at base line will be compared to those taken 1 and 6 months later.

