9.1 Sample Size

With a sample size of N=15 patients we should be able to detect changes of around the same order of magnitude as the variability in those differences (delta/sigma=1) with greater than 90% power on a one-sided test at the 5% level of statistical significance.

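### Section 9.2 tests three outcomes under the primary heading, one of them a secondary endpoint, without control across them or a rule for when the two leg volumes disagree

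*Protocol*

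**What the plan says.** **Endpoint definitions.** Protocol section 2.3 gives a single primary endpoint: "Change in skeletal muscle bulk within both lower limbs between baseline, 1 month and 6 months, using compressed sensing (accelerated) MRI". The table in section 2.5 agrees. Spectroscopy is a secondary endpoint in section 2.4c: "Magnetic resonance spectroscopy of skeletal muscle: content of creatine, phosphocreatine and inorganic phosphate at baseline, 1 month and 6 months". The synopsis and the section 2.5 table name the creatine-to-water ratio itself, also as secondary.

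**Measurement.** Section 7.3.2 says that "the total skeletal muscle volume in the upper and lower leg, covering both legs will be measured". It then gives separate bony landmarks for the upper-leg and the lower-leg volume. The synopsis describes the primary measurement as "accelerated MRI of selected limb/compartment", and the schedule of events in section 6.1 also speaks of a selected limb.

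**Analysis.** Section 9.2, headed Primary Endpoint Analysis, lists two volumes (lower leg and upper leg, both legs) and one spectroscopic ratio, and concludes: "There are therefore three outcome measures at three time points for each of 15 individuals". Each is assessed by its own one-way repeated-measures ANOVA, with Friedman's test as the fallback. On the ANOVA route, post-hoc comparisons of time points follow only if the ANOVA is significant, and they are Bonferroni-corrected. No significance level is given for the ANOVAs. The only level in the protocol is in section 9.1: 5%, one-sided.

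**The concern.** The endpoint sections and the analysis section do not describe the same primary analysis. Sections 2.3 and 2.5 have one primary quantity. Section 9.2 has three test results under the primary heading, and one of them belongs to a secondary endpoint.

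Two things follow. First, the correction covers time points within an outcome but not the outcomes themselves, so the chance of at least one false positive exceeds the nominal level. Second, the primary objective (section 2.1) asks whether muscle bulk changes. If the upper-leg volume changes and the lower-leg volume does not, or if only creatine/water moves, the plan gives no rule for answering it. The closing paragraph of section 9.2 makes further work depend on a significant change in muscle volume, without saying whether one segment suffices.

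The protocol says the data will be used to power a controlled trial. If the most favourable of several results is carried forward, the assumed effect tends to be too large and the next trial too small.

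**Working it through.** **1. The plan's own figure.** Inputs from section 9.1: n = 15, mean change divided by SD of change = 1, one-sided 5%, power stated as "with greater than 90% power". For a paired t-test the noncentrality is √15 = 3.873.
- Normal approximation: Φ(3.873 − 1.645) = Φ(2.228) = 98.7%.
- Noncentral t with 14 degrees of freedom: 97.9% one-sided, 94.9% two-sided.

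The stated power reproduces and is not in dispute. It describes one paired comparison, not the set of ANOVAs in section 9.2.

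**2. Error across independent outcomes.** The 5% level is carried over from section 9.1.
- Two volumes: 1 − 0.95² = 9.75%.
- Two volumes plus creatine/water: 1 − 0.95³ = 14.26%.

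**3. Error across correlated outcomes.** The protocol gives no correlations, so a range is assumed. The simulation used n = 15, three time points, no true change, one repeated-measures ANOVA F test per outcome at 5%, and 100,000 trials per setting. Entries are the chance of at least one significant ANOVA; r is the correlation between the within-patient errors of two outcomes.

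| r between the two volumes | Two volumes only | All three, creatine/water r = 0 | All three, creatine/water r = 0.3 | All three, creatine/water r = 0.5 |
|---|---|---|---|---|
| 0 | 9.65% | 14.11% | not run | not run |
| 0.5 | 9.26% | 13.73% | 13.33% | 12.79% |
| 0.7 | 8.50% | 13.14% | 12.85% | 12.19% |
| 0.8 | 8.09% | 12.62% | 12.15% | 11.75% |
| 0.9 | 7.04% | 11.68% | 11.73% | 11.18% |

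So the error is about 7-10% for the two volumes and about 12-14% for all three. The latter falls to about 11% when the volumes correlate 0.9 and creatine/water correlates 0.5 with both.

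**4. Effect of the remedies.** One primary outcome tested at 5% has an error of 5%. The alternative is Bonferroni over three outcomes, 0.05/3 = 0.0167 each. Its simulated familywise error is 4.0-4.9% over the settings in the table. For a single paired comparison at n = 15 and standardised change 1, power is:

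| Level | One-sided | Two-sided |
|---|---|---|
| 0.05/3 | 92.2% | 85.8% |
| 0.05/9 | 81.0% | 71.4% |

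On the protocol's one-sided basis, correcting for three outcomes keeps power above 90%. The case for a single primary measure therefore rests on having one answer to the primary objective, not on a large saving of power.

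**The case against.** The best counter-argument is that the endpoint sections are consistent and should govern. The synopsis and sections 2.1, 2.3 and 2.5 all put muscle bulk first and spectroscopy second. Section 9.2 never calls the three measures primary, and its last paragraph speaks of muscle volume and creatine/water as separate things. It is also the only analysis section besides sample size, so its heading may simply be too narrow. This stands in part: a reader might infer that the plan has a 12-14% false-positive rate for its primary claim, but that holds only if creatine/water is claimed as primary. If section 2.3 governs, the figure is about 7-10%. Nor does section 9.2 itself set 5%; that level comes from a one-sided test in section 9.1, which does not correspond to an omnibus F test.

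Three further inferences are tempting and not supported.
- **That the two follow-up times add more uncontrolled chances.** On the ANOVA route one omnibus test covers all three time points, and the corrected post-hoc tests follow only if it is significant. The percentages above count omnibus tests only. Leaving the primary time point open is acceptable in a preliminary study.
- **That section 7.3.2 contradicts section 9.2 by promising only a total.** The same paragraph defines the two segments separately, as section 9.2 uses them. It shows that a total is available, not that segments are excluded.
- **That multiplicity control would wreck the power.** A fall to 71% needs two-sided tests and division by nine; the protocol states a one-sided test.

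It is also fair that this is an uncontrolled 15-patient study, that section 9.2 calls it a pilot, and that a multiplicity rule could sit in a SAP not seen here. That lowers the severity. It does not remove the mismatch between sections 2.3 to 2.5 and section 9.2, which is in the protocol itself. The selected-limb wording is editorial, since sections 2.3, 7.3.2 and 9.2 agree on both legs.

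**Conclusion.** The point holds in moderate form. Section 9.2 places a secondary endpoint under the primary heading, splits the one primary endpoint into two separately tested volumes, and neither controls error across them nor says how they combine.

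The chance of at least one false positive is about 7-10% if only the volumes count and about 12-14% if creatine/water counts too. This rests on the 5% level borrowed from section 9.1, on ANOVA assumptions being met, and on assumed correlations of 0 to 0.9. That the figure depends on which section is followed is part of the defect.

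This is a should-fix. The study is a small single-arm pilot and its stated power is correct as far as it goes, but its primary objective needs one defined answer before the result is used to plan a trial.

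**What to change.** - **Section 9.2:** make total skeletal muscle volume (upper plus lower leg, both legs, as measured under section 7.3.2) the single primary measure. Keep the two segment volumes as supportive analyses and state the significance level.
- **Creatine/water:** move it to a secondary analysis, in line with sections 2.4c and 2.5.
- **Synopsis and schedule of events:** replace the selected-limb wording with both legs, to match sections 2.3, 7.3.2 and 9.2.
- **Optional:** name one primary time point, such as 6 months. The omnibus ANOVA with Bonferroni post-hoc tests already covers time, so this is a preference.

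The cost is a protocol wording change. The total is the sum of volumes already measured, so no scan or visit is added. The downside is that a change confined to one segment is diluted in the total and would be seen only in the supportive analysis.

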6.8 Withdrawal criteria

Participants may withdraw from the study at any point without the requirement for any further involvement. If a participant wishes to withdraw from certain aspects of follow-up (e.g. repeat muscle biopsy) but to continue with other study assessments, this will be

permitted and encouraged. The PI may also withdraw patients from the study for medical reasons.

Participants who fail screening will be replaced but participants who drop out after the baseline visit will not be replaced. Where there is appropriate consent, their data will be used within the study report.

Participants who discontinue tofacitinib after visit 4, for whatever reason, will be invited to attend for an early withdrawal visit at the earliest opportunity. Participants will be encouraged to undergo the full range of study assessments if willing to do so but, if a participant wishes to decline some procedures but undergo others, this will be permitted and encouraged. Participants may also decline an early withdrawal visit in toto. At the discretion of the PI, aspects of the early withdrawal visit may be omitted depending on the time interval since they were last performed.

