6.9 Changes to treatment

Tofacitinib will be prescribed as 5mg twice daily, the approved dose for rheumatoid arthritis.

If there are adverse effects relating to tofacitinib, the PI may discontinue the drug for 1 week before restarting, potentially at a dose of 5mg once daily with subsequent escalation to 5mg twice daily, subject to PI's discretion.

In the event of unforeseen events such as intercurrent illness or surgery, it may be necessary for participants to temporarily suspend tofacitinib and other medications and this will be managed as per standard clinical practice.

If participants have significant persisting arthritis symptoms, adjustments to background DMARD therapy are permitted at PI's discretion. Two intra-articular glucocorticoid injections are permitted (two on one occasion or one on two occasions). If additional escape therapy is required, such as substitution of an alternative JAK inhibitor or biologic therapy, or administration of oral or IM glucocorticoid, the participant will be withdrawn from the study and an early withdrawal visit triggered.

Any adjustments to treatment such as those described above will be managed according to standard clinical practice and documented at the study visits.

7 Study Procedures

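### Section 9.2 fixes a three-visit ANOVA that leaves out incomplete scan series, which the protocol's own withdrawal rules make likely

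*Protocol*

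**What the plan says.** Section 9.2 of the Protocol treats the data as complete: "There are therefore three outcome measures at three time points for each of 15 individuals". Each measure (upper-leg volume, lower-leg volume, soleus creatine/water ratio) goes to a one-way repeated-measures ANOVA, or to Friedman's test if the assumptions fail. Bonferroni-corrected comparisons follow a significant ANOVA. SPSS 24 is named.

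Section 9.1 gives the sample-size basis: "With a sample size of N=15 patients", a change equal to one SD of the differences can be detected "with greater than 90% power" "on a one-sided test at the 5% level of statistical significance". It makes no allowance for loss.

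Section 6.8 says that participants lost after baseline are not replaced, that single procedures may be declined, and that the early-withdrawal visit may be declined altogether. It adds: "Where there is appropriate consent, their data will be used within the study report". It also says: "Participants who discontinue tofacitinib after visit 4, for whatever reason, will be invited to attend for an early withdrawal visit".

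Section 6.9 deals with persisting arthritis symptoms. If escape therapy is needed (another JAK inhibitor, a biologic, oral or IM glucocorticoid), "the participant will be withdrawn from the study and an early withdrawal visit triggered".

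The schedule in section 6.1 lists MRI, MRS, DEXA and biopsy at early withdrawal. A footnote limits repeats to cases where at least 3 weeks have passed since the original imaging or biopsy.

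**The concern.** Repeated-measures ANOVA and Friedman's test both work on complete rows. A participant with baseline and 1-month scans but no 6-month scan drops out of the test entirely, so even the observed 1-month change is lost. The protocol foresees such participants but fixes a method that cannot use them.

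One route out of the study, escape therapy, is tied to persisting disease. The hypothesis in sections 1.2 and 1.3 links muscle gain to interrupted inflammatory signalling. If it is right, those who leave by this route are the ones expected to gain least, and the remaining completers would show too large a 6-month change. There is no control arm to offset this. Section 3 says the data will be used to power a controlled trial, so an overstated change would feed into that sample size.

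**Working it through.** **1. The plan's own figure.** Inputs from section 9.1: n = 15, delta/sigma = 1, one-sided 5%. Take a paired t-test with n - 1 df and noncentrality √n × delta/sigma = √15 = 3.87. Power is 97.9%, so the stated figure of more than 90% holds for 15 complete pairs. On the same test it is 94.5% at 12 completers, 92.5% at 11 and 89.8% at 10.

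**2. Who enters the stated test.**

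| Scans available | Used by ANOVA or Friedman | Usable by a mixed model |
|---|---|---|
| Baseline, 1 month, 6 months | yes | yes |
| Baseline, 1 month | no | yes |
| Baseline, 1 month, early withdrawal | not stated | yes, plus the extra scan at its actual time in a sensitivity analysis |

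**3. Size of the bias, by formula.** The Protocol gives no drop-out rate, so the loss d is assumed to be 20% or 30%. Let rho (assumed) be the correlation between the tendency to stay and the 6-month change. If those lowest on that tendency leave, the completers' mean is shifted by rho × phi(q)/(1 - d) SD, where q is the normal quantile of d.
- d = 20%: phi(-0.842) = 0.280, and 0.280/0.8 = 0.350. With rho = 0.3 the shift is 0.105; with rho = 0.5 it is 0.175.
- d = 30%: phi(-0.524) = 0.348, and 0.348/0.7 = 0.497. With rho = 0.3 the shift is 0.149; with rho = 0.5 it is 0.248.
- rho = 0 gives no shift; a negative rho gives a negative shift.

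**4. Size of the bias, by simulation.** Assumed: n = 15, true 6-month change 1.0 SD, correlation of 1- and 6-month changes 0.5-0.7, logistic withdrawal with slope -2 per SD, 6,000 replicates. The likelihood column stands for an analysis that also uses the 1-month data.

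| What drives withdrawal | Loss | Complete cases | Likelihood |
|---|---|---|---|
| 1-month muscle change | 20% | 1.14-1.19 | 1.00 |
| 1-month muscle change | 30% | 1.19-1.27 | 1.00 |
| Latent arthritis response, correlation 0.3 with muscle change | 20-30% | 1.08-1.11 | 1.03-1.05 |
| The unseen 6-month change itself | 20% | 1.26-1.27 | 1.15-1.21 |
| Nothing (random loss) | 20% | 1.00 | 1.00 |

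The standard error at 20% random loss is about 0.29 SD for complete cases and 0.28-0.29 for the likelihood analysis.

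**5. What carries forward.** Sample size varies as 1/delta². If the next trial took an overstated change at face value, it would be too small by 1 - 1/1.08² = 14% to 1 - 1/1.11² = 19% in the milder case. In the case driven by the 1-month change, the range is 1 - 1/1.14² = 23% to 1 - 1/1.27² = 38%. These are conditional on the assumptions in step 4.

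**The case against.** Several stronger readings are tempting, and the documents do not support them.

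- **Every withdrawn participant is discarded.** The schedule provides MRI at early withdrawal, and the Protocol neither allows nor forbids that scan as the final measurement. Exclusion is certain only if it may not stand in, or if it is declined or not done.
- **The result is biased upward.** The direction rests on the trial's own untested hypothesis. Participants may also leave by choice, after adverse effects or for medical reasons, and none of these has a stated direction. Background DMARD adjustment and two intra-articular injections are permitted without withdrawal. Someone who declines only the biopsy stays in the MRI analysis.
- **Section 9.2 contradicts section 6.8.** Section 6.8 promises use within the report, not in the primary test. Descriptive reporting would honour it, as would the individual-patient data mentioned in section 2.4. This is a tension only.
- **Lost power is a reason for the mixed model.** Two-sided Bonferroni power (0.05/3) does fall from 85.8% at 15 to 73.0% at 12. That comes from losing people, and step 4 shows the mixed model recovers almost none of it.

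It is also fair to say that missing-data rules often sit in an SAP, that this is a 15-patient pilot, and that the milder bias of about 0.1 SD is small beside a standard error near 0.29 SD. What remains is that 9.2 does more than stay silent: it names two methods that cannot use a partial series.

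**Conclusion.** The point holds as a should-fix. The stated primary method suits 15 complete series, while sections 6.8 and 6.9 make fewer than 15 likely. Partial series are wasted, and early-withdrawal scans have no assigned role. If loss is related to response, the completers' 6-month change is overstated by about 0.1 SD (withdrawal correlated 0.3 with muscle change) up to 0.14-0.27 SD (withdrawal driven by the 1-month change). If loss is unrelated, there is no bias. The loss rates, correlations and withdrawal models are assumptions, since the Protocol gives none.

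There is also a minor mismatch. Section 6.8 ties the early-withdrawal invitation to stopping tofacitinib after Visit 4, while section 6.9 triggers the visit on escape therapy without naming a visit. The footnote's 3-week limit, if it counts from the baseline procedures, matters only before Visit 4. The passages can be read together but should be reconciled.

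**What to change.** In section 9.2, replace the repeated-measures ANOVA with a linear mixed model (SPSS MIXED, REML, visit as fixed factor, unstructured within-participant covariance, Satterthwaite df). Include every participant with a baseline scan and all available scheduled scans. Report the 6-month change with a 95% CI. Use early-withdrawal scans at their actual time in a sensitivity analysis. Reconcile sections 6.8, 6.9 and the schedule footnote on who is offered the early-withdrawal assessments.

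The cost is a few sentences: no new data are needed and the software is already named. The model is slightly more complex and relies on data missing at random. It removes only part of the bias if withdrawal depends on unobserved factors, and it restores little of the power lost to drop-out.

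### Section 9.2 sends a sphericity failure alone to Friedman's test, where a Greenhouse-Geisser correction would hold the error rate and keep the analysis in cm³

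*Protocol*

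**What the plan says.** Section 9.2 of the protocol applies one procedure to two muscle volumes and the creatine-to-water ratio: "There are therefore three outcome measures at three time points for each of 15 individuals". Each measure is first screened ("checks for outliers, normality, homogeneity and sphericity"). If it passes, a one-way repeated-measures ANOVA is run, with Bonferroni-corrected comparisons if that is significant. If it does not pass, the plan reads: "In the event that the data do not satisfy the criteria for one-way repeated ANOVA, then Friedman's ANOVA will be performed". Comparisons between visits on this second branch take a different form from the Bonferroni ones, the rank test being "followed by step-wise post-hoc tests to identify which timepoints are significantly different".

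The text does not distinguish which check failed, and it names no epsilon correction. On both branches it adds: "Effect sizes will be calculated". It does not say of what type or on what scale.

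Section 9.1 states that N=15 detects a change of one SD of the differences "with greater than 90% power on a one-sided test at the 5% level of statistical significance". Section 3 gives the purpose of the data: to power a later controlled trial.

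**The concern.** Sphericity means that the three pairwise differences (baseline to 1 month, baseline to 6 months, 1 to 6 months) have equal variance. It says nothing about the shape of the distribution. When it fails, the ordinary F test rejects too often. The usual remedy is to shrink its degrees of freedom by an estimate of epsilon, which leaves the data on their own scale. Section 9.2 instead replaces volumes by ranks 1 to 3 within each patient, and so discards how large each change was.

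The visits are unevenly spaced, at 0, 1 and 6 months. A 1-month change could well vary less than a 6-month change, and that alone breaks sphericity. A branch that reads like a rare fallback could then become the usual primary analysis. At stake are power at N=15 and a clear route to a mean change and SD in cm³, which the planning of the later trial needs.

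**Working it through.** **1. The plan's own figure.** Inputs from section 9.1: n=15, delta/sigma=1, one-sided 5%. For a paired t test the noncentrality is √15 × 1 = 3.873 on 14 degrees of freedom, which gives power of 97.9% (two-sided: 94.9%). The claim of more than 90% therefore reproduces, but for one paired comparison and not for the procedure in section 9.2.

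**2. Assumptions for the check.** The protocol gives no SD or correlation for muscle volume and does not name its sphericity test. Assumed: Mauchly's test at 5%; 6-month change with SD 1; normal data; 6-month effect of 1 SD unless stated otherwise.

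**3. Epsilon when the 1-month change has half the SD.** Take difference variances of 0.25 (baseline to 1 month), 1 (baseline to 6 months) and 1 (1 to 6 months).
- Covariance of the two changes from baseline: (0.25 + 1 − 1)/2 = 0.125.
- Variance of the contrast (baseline − 1 month)/√2: 0.25/2 = 0.125.
- Variance of the contrast (baseline + 1 month − 2 × 6 months)/√6: (0.25 − 4 × 0.125 + 4 × 1)/6 = 0.625.
- The covariance of the two contrasts is proportional to 0.25 − 2 × 0.125 = 0.
- Epsilon = (0.125 + 0.625)² / [2 × (0.125² + 0.625²)] = 0.5625/0.8125 = 0.69.

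**4. Simulation at that covariance** (20,000 datasets per setting). The sphericity check rejects in about 72% of datasets. Omnibus power, with each test applied to every dataset:

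| Effect at 1 month (SD of 6-month change) | Greenhouse-Geisser | Friedman |
|---|---|---|
| 0 | 96% | 87% |
| 0.2 | 93% | 84% |
| one third | 92% | 86% |
| one half | 92.7% | 92.4% |

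Under the null, the two-stage procedure (Friedman if the check rejects, uncorrected F if not) has a type I error of 5.9%.

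**5. Dependence on the covariance** (40,000 datasets per setting; Greenhouse-Geisser is GG):

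| SD of 1-month change, correlation with 6-month change | Epsilon | Check rejects | GG / Friedman, no 1-month effect | GG / Friedman, one third at 1 month | Type I error: uncorrected F / GG / Friedman |
|---|---|---|---|---|---|
| 1, 0.5 | 1.00 | 5% | 96.9% / 90.0% | 91.8% / 81.2% | 5.1% / 4.4% / 4.6% |
| 0.5, 0.5 | 0.70 | 71% | 97.7% / 91.3% | 93.9% / 86.8% | 7.1% / 5.1% / 5.1% |
| 0.3, 0.3 | 0.57 | 99% | 96.1% / 87.1% | 92.0% / 94.5% | 8.2% / 5.2% / 5.3% |

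With a 6-month effect of 0.8 SD added (one third of it present at 1 month), Friedman has less power than Greenhouse-Geisser in 7 of 9 normal-data scenarios, by 6.4 to 13.3 points. It has more in 2, by 2.5 to 4.3 points.

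**6. Cost within the switched datasets.** Power in step 4 is for a test used throughout. At epsilon 0.70, looking only at datasets that the check diverts:
- No 1-month effect: GG 97.1%, Friedman 89.5%, a difference of 7.6 points.
- One third at 1 month: GG 92.5%, Friedman 84.9%, again 7.6 points.

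With 71% diverted, the switch costs 0.71 × 7.6 = 5.4 points of omnibus power relative to correcting those same datasets.

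**The case against.** Friedman's test is a conventional and valid fallback for non-normal data or outliers, and section 9.2 screens for both. With heavy-tailed changes (t with 3 degrees of freedom) it had more power than Greenhouse-Geisser in all 9 scenarios, by 3.0 to 14.3 points. This stands. A reader might infer that the rank fallback is wrong for every trigger; the protocol does not support that, and the point is confined to sphericity. One caution remains on that branch. With skewed changes of zero mean, Friedman rejected in 21% to 27% of datasets and Greenhouse-Geisser in 6% to 10%, because a rank test does not test mean change.

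The protocol states no variances, so nobody can say from it that sphericity will fail. This also stands: the 72% is conditional, and the power loss can vanish or reverse.

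A reader might blame Friedman for the whole gap between the power in section 9.1 and the power to declare a 6-month change under section 9.2. Most of that gap has another source. A Greenhouse-Geisser gate followed by Bonferroni comparisons reaches about 86%, against 94.9% for a single two-sided paired test, with no rank test involved.

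A reader might also take the uncorrected F's 7.1% or 8.2% as the plan's error rate. It is not, since the plan abandons that F whenever the check rejects.

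Nor does the plan rule out an estimate in cm³: effect sizes are promised on both branches, and an analysis plan that is not shown may define them. What remains is that section 9.2 itself fixes the switch, so it is not a detail left for later.

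**Conclusion.** The point holds for a failure of sphericity with otherwise well-behaved data. There Friedman's test is the wrong remedy: it discards magnitudes to solve a problem that a degrees-of-freedom correction already solves, with type I error of 5.1% to 5.2% in the non-spherical settings examined.

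Under the central assumption (1-month SD half the 6-month SD, normal data, n=15) about 72% of datasets switch. Omnibus power is 84-87% against 92-96% when the 1-month effect is 0 to one third of an SD, and equal for practical purposes when it is one half. The inflation of type I error is small, at about 5.9%.

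The direction and size of the power difference depend on a covariance that the protocol does not give. The choice of remedy does not depend on it. This is a cheap improvement to a pilot study's analysis and no threat to its validity.

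**What to change.** In section 9.2:
- Remove sphericity from the criteria that lead to Friedman's test.
- Always report the repeated-measures F with the Greenhouse-Geisser correction, whatever the sphericity check shows.
- Keep the rank test for marked non-normality or outliers only.
- On either branch, report the change in muscle volume in cm³ at 1 and 6 months with its SD and confidence interval, and do the same for the creatine-to-water ratio on its own scale.

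This takes a sentence or two, and the correction is part of standard software output. The cost is a slightly conservative F when sphericity does hold: type I error 4.4% instead of 5.1%, and power 91.8% instead of 92.9% with one third of the effect at 1 month.

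Two larger changes do not follow from this point. Making a baseline-to-6-month contrast the sole primary test would drop the 1-month part of the endpoint in section 2.3. Deleting the rank fallback altogether would remove protection against outliers at N=15. Both are trade-offs for the investigators.
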